8.3 Flow Cytometric Analyses of Lymphocyte Subsets

Number of CD33⁺CD11b⁺HLA-DR^{-or dim} IMCs, other myeloid cells (including CD33⁺CD11b⁺HLA-DR⁺ cells), CD4⁺, CD8⁺ T cells and CD4⁺/Foxp3⁺ T regulatory cells at serial time points pre- and post-vaccines will be evaluated. These data will be evaluated in an exploratory manner.

8.4 Evaluation of Tumor Infiltrating Leukocytes (TILs)

We will evaluate TILs in tumor tissues obtained from patients who received pre-surgical treatment with the IMA950+poly-ICLC vaccine with or without varillumab.

We will isolate TILs and evaluate whether surgically resected tumors from Arm 1 (IMA950+poly-ICLC vaccine **with** varlilumab) patients demonstrate significantly higher levels of vaccine-reactive T-cells and CXCL10 expression compared with:1) those resected from Arm 2 (IMA950+poly-ICLC vaccine **without** varlilumab) patients; and 2) HLA-A2+ patients who underwent resection under IRB# 15-17078 vaccine study.

We will also compare T-cell clonotypes of TILs with those in post-vaccine PBMC. Specifically, we will determine whether T-cell clonotypes that are reactive to IMA950 peptides in PBMC are found in TILs. To this end, IMA950-specific multimer-positive T-cells in post vaccine PBMC will be sorted, and T-cell receptor β-chain usage in those populations will be determined. Then, we will evaluate whether those T-cell populations are increased in TILs obtained from Arm 1 patients compared with those obtained from Arm 2 (and IRB# 15-17078 vaccine study) patients. This method is expected to be more sensitive than traditional multimer-based analysis.

We will also perform multi-color flow cytometry to characterize infiltrating T-cells in terms of their number, phenotype, and reactivity to IMA950 peptides by 6-hr *in vitro* re-stimulation with IMA950 peptides followed by staining of cytoplasmic IFN-γ. These studies will allow us to evaluate whether vaccine-induced T-cells efficiently traffic to the brain tumor site and maintain their function and viability. We will also evaluate the number and phenotype of CD33+CD11b+HLA-DR-or dim immature myeloid cells (IMCs) and other myeloid cells (including CD33+CD11b+HLA-DR+ cells) in TILs. RT-PCR will be applied to evaluate the

12 April 2020 Page 62 of 88 confidential

expression of chemokines, such as CXCL10, and immuno-regulatory substances, such as arginase-1.

9 Measurement of Effect

9.1 Primary Objectives

9.1.1 Safety

We will determine whether it is safe to administer pre-surgical IMA950+poly-ICLC in combination with varlilumab in patients with WHO grade 2 gliomas in whom surgical resection of tumor is clinically indicated.

Endpoints will therefore include incidence and severity of adverse events, using standard criteria as well as close clinical follow-up as would be performed normally in this group of participants following vaccinations. All reported or observed toxicities and adverse events at all clinic visits will be graded, documented and reported according to a standard toxicity table, the Common Terminology Criteria for Adverse Events (CTCAE) version 5.0 (http://ctep.cancer.gov/protocolDevelopment/electronic_applications/ctc.htm#ctc_40). We will consider the regimen is unacceptably toxic if the >33% of patients develop RLT (see Section 5.6). A participant who receives the scheduled pre-surgical vaccines, surgical resection and whose tumor is found to be WHO grade II glioma will not be replaced. If the scheduled surgery is delayed longer than 2 weeks for a toxicity or any vaccine dose is delayed for 5 weeks or longer for any reason, those patients are considered to have gone off-study due to RLT even if the toxicities/AEs do not meet the criteria of RLT defined in Section 5.3.1.

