5.6 Definition of Regimen Limiting Toxicities (RLT) and Suspension of Enrollment

5.6.1 Definition of RLT

Toxicity will be determined using the revised NCI Common Toxicity Criteria version 5.0 for Toxicity and Adverse Event Reporting (CTCAE) (http://ctep.info.nin.gov).

Management and dose modifications associated with the above adverse events are outlined in Section 5.7.

Participants will be observed for regimen limiting toxicity (RLT) throughout the study. The following are considered to be RLTs if they are judged possibly, probably or definitely associated with treatment. Should they occur, individual participants will be taken off study and no further injections will be given.

- Grade 2 or more any infusion reaction except for Grade 2 pain
- Grade 2 or more cytokine release syndrome
- Grade 2 or more bronchospasm or generalized uticaria (hypersensitivity)
- Grade 2 or more allergic reaction, such as exfoliative erythroderma, anaphylaxis, or vascular collapse
- Grade 2 or more autoimmune disease (e.g. hypothyroidism, autoimmune encephalitis)
- Any Grade 3 or more toxicity possibly, probably, or definitely related to the vaccine or Varlilumab with particular attention to the following events.

The following are also considered RLTs:

- Dosing delays > 6 weeks for IMA950+poly-ICLC vaccines or varillumab (Arm 1 patients only) administration.
- Delay of the scheduled surgical resection for longer than 2 weeks possibly, probably or definitely related to toxicity of the study treatment.

The following are NOT considered RLTs:

- Grade 3 nausea, vomiting, or diarrhea that resolves to ≤ grade 1 with or without treatment within 48 hours
- Grade 3 flu-like symptoms that resolve within 24 hours with the use of acetaminophen 650-1000 mg or with any NSAID

5.6.2 Events Which Will Temporarily Halt Enrollment at Any Time:

Certain events will be considered unacceptable and a single occurrence will lead to temporary closure of enrollment while under review for attribution to study therapy (not related to surgical procedures):

- The occurrence of grade 3 or 4 toxicity, excluding local skin reaction and flu-like symptoms in 3 patients
- Toxicity requiring the use of pressors, including grade 4 vascular leak syndrome or grade 3 and 4 hypotension
- Toxicity requiring ventilation support, including grade 4 respiratory toxicity

12 April 2020 Page 38 of 88 confidential

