5.7 Drug Administration Delay, Dose Reduction, and/or Discontinuation (Individual Patients)

5.7.1 Delay in treatment administration

Treatment will be delayed by 1 week if on the day of the planned vaccination

- Patient has a fever of > 101°F (38.3 °C)
- Treatment related side effects have not resolved to grade 1 or better (except for grade 2 lymphopenia and injection site reactions from prior IMA950+poly-ICLC vaccine).

If the continued inflammatory reactions at the injection site remain too severe in both legs to allow subsequent vaccines, the treatment will be suspended for up to 6 weeks from the originally scheduled date for the next vaccine. When the therapy is resumed after a delayed dose, subsequent schedules will be slid back to keep the original intervals. If the situation does not resolve in 6 weeks, this is considered RLT and the patient will be withdrawn from the protocol.

Vaccination will be held for any \geq Grade 2 non-RLT AE (except grade 2 lymphopenia or flu-like symptoms), felt to be related to therapy, until they return to \leq Grade 1.

Possible adverse events by IMA950-poly-ICLC vaccines and varillumab are summarized in Section 5.8. In circumstances where assessment of an adverse event is limited, such as by intercurrent illness, or when laboratory studies are required to assess for other causes of toxicity, the treatment schedule may be interrupted for up to 6 weeks. Delay of one vaccine (and varillumab if scheduled) administration by up to 6 weeks will not be considered a protocol violation if due to an adverse event, regardless of attribution. If one or more treatment cycle is delayed by longer than 6 weeks due to an adverse event, regardless of attribution, treatment must be discontinued.

In the case of hepatic enzyme elevation >4x baseline (which is Grade 2; 3-5 x ULN), or any other unforeseen intolerable side effects of grade 2 (except for flu-like symptoms) or greater but not meeting the RLT criteria in Section 5.3.1, IMA950-poly-ICLC vaccine will be discontinued until that toxicity has reduced to Grade 1 or less. If the vaccine cannot be reinitiated in 6 weeks, the participant will be withdrawn for the RLT.

In the pre-surgical phase:

 If the scheduled craniotomy is delayed longer than 2 weeks secondary to RLT, the patient will be withdrawn from the protocol

12 April 2020 Page 39 of 88 confidential

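### The vaccine-delay limit that makes a patient an RLT differs between sections (5 versus 6 weeks), and a related grade 2 infusion reaction ends treatment in 5.6.1 but is re-infused under 5.8.4

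*Combined protocol and SAP*

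**What the plan says.** **Delay.** Section 9.1.1 states that if "any vaccine dose is delayed for 5 weeks or longer for any reason, those patients are considered to have gone off-study due to RLT", and adds that this holds even when the RLT criteria are not met. Section 5.6.1 lists as an RLT "Dosing delays > 6 weeks for IMA950+poly-ICLC vaccines" (or varlilumab), with no attribution condition on that bullet. Section 5.7.1 uses 6 weeks twice. For injection-site reactions: "If the situation does not resolve in 6 weeks, this is considered RLT and the patient will be withdrawn from the protocol". For hepatic enzyme elevation and other grade 2 or higher non-RLT toxicity: "If the vaccine cannot be reinitiated in 6 weeks, the participant will be withdrawn for the RLT". It also says that delay of one "administration by up to 6 weeks will not be considered a protocol violation if due to an adverse event, regardless of attribution", and "When the therapy is resumed after a delayed dose, subsequent schedules will be slid back to keep the original intervals". Section 5.7.3 discontinues vaccination for a delay greater than 6 weeks.

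**Infusion reaction.** Section 5.6.1 lists "Grade 2 or more any infusion reaction except for Grade 2 pain" as an RLT if at least possibly related to treatment, and then "individual participants will be taken off study and no further injections will be given". Sections 5.7.3 and 5.10 also end treatment on an RLT. For grade 2 symptoms, section 5.8.4 restarts an interrupted infusion at 50% of the original rate, allows a return to 100% after 30 minutes without complications, and recommends premedication before later varlilumab doses. It requires permanent discontinuation only for grade 3 or 4.

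**Where RLT is used.** Section 12.1.1 tabulates the RLT proportion per arm with exact intervals and compares the arms by Fisher's exact test. Section 12.2 counts RLTs for the stopping rule. Section 12.1.1 cites section 5.3.1 for the definition, which is in 5.6.1.

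**The concern.** A patient whose dose is 5 to 6 weeks late is an RLT taken off study under 9.1.1, and a patient who may resume under 5.6.1 and 5.7.1. Because 9.1.1 says any reason, a scheduling delay would also be recorded as toxicity. The count feeds a co-primary endpoint and the stopping rule. A removal before the fourth post-surgery vaccine also makes the patient non-evaluable for the immunological endpoint and replaced (4.3), so the other co-primary population is affected too.

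For infusion reactions the problem is re-dosing, not counting. Staff who follow 5.8.4 would re-expose a patient whom 5.6.1 removes. Section 5.8.5 itself warns that this combination may cause events not seen with the separate agents.

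**Working it through.** **1. Delay rules side by side.**

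| Section | Limit | Cause required | Consequence |
|---|---|---|---|
| 9.1.1 | 5 weeks or longer | any reason | off study due to RLT |
| 5.6.1 | more than 6 weeks | none stated | RLT |
| 5.7.1, two RLT rules | not resolved or restarted in 6 weeks | toxicity | RLT, withdrawn |
| 5.7.1, general rule | longer than 6 weeks | adverse event, any attribution | treatment discontinued |
| 5.7.3 | greater than 6 weeks | treatment-related toxicity or RLT | vaccination discontinued |

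A delay from 5 up to 6 weeks is treated differently in 9.1.1 and everywhere else. No section ranks one rule above another.

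**2. Infusion rules side by side, for a related grade 2 reaction at the first infusion (D-23).** Five varlilumab infusions are planned (7.3), so 4 remain (A1, A7, A13, A19). Vaccines remaining: 3 before surgery + 8 after = 11.

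| | 5.6.1 and 5.7.3 | 5.8.4 |
|---|---|---|
| Interrupted infusion | not resumed (patient off study) | restarted at 50% rate |
| Later infusions | 0 of 4 | up to 4, with premedication |
| Remaining vaccines | 0 of 11 | not stopped by this section |

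**3. The plan's stopping table.** Section 12.2 uses a Beta(0.09, 1.71) prior and stops if P(pRLT > 0.33) > 0.33. The prior mean is 0.09/(0.09 + 1.71) = 0.05 and the prior P(pRLT > 0.33) is 0.050, as stated. Taking the smallest r for which P(p > 0.33 | Beta(0.09 + r, 1.71 + n − r)) > 0.33 reproduces all 13 printed entries: 2 RLTs at n = 3–5, 3 at 6–9, 4 at 10–12, 5 at 13–15.

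**4. Effect of the delay conflict on stopping.** The documents give no rate for 5-to-6-week delays. Let d be the proportion of patients with such a delay counted as RLT, independent of other RLTs. The combined rate is p′ = 1 − (1 − 0.05)(1 − d). The one-arm stopping probability s comes from an exact recursion over patients 1 to 15 with the printed boundaries. Stopping in either of two independent arms is 1 − (1 − s)².

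| d | p′ | s, one arm | either arm | s if the first 3 patients have no such delay | expected RLTs, 15p′ |
|---|---|---|---|---|---|
| 0 | 0.0500 | 0.026 | 0.052 | 0.026 | 0.75 |
| 0.02 (assumed) | 0.0690 | 0.050 | 0.098 | 0.038 | 1.04 |
| 0.05 (assumed) | 0.0975 | 0.101 | 0.191 | 0.060 | 1.46 |

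The columns with a constant rate are upper limits. Pre-surgery doses are weekly, and a surgery delay beyond 2 weeks has its own rule, so a 5-to-6-week vaccine delay realistically arises only after surgery. The increase in one-arm stopping runs from 0.0375 − 0.0263 = 0.011 to 0.1008 − 0.0263 = 0.075.

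**5. Effect on the tabulated endpoint.** With 15 patients and pRLT = 0.05, P(0 RLTs) = 0.95¹⁵ = 0.46, the most likely count. One reclassified patient moves the arm from 0/15 (Clopper-Pearson 95% interval 0 to 22%) to 1/15 = 6.7% (0.2% to 32%).

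**The case against.** On delay, 9.1.1 can be read as a disposition rule that deems certain patients off study without meeting the RLT criteria. Section 12.1.1 uses the same stale 5.3.1 pointer as 9.1.1, and 9.1.1 elsewhere cites section 5.6 correctly, so the analysis count arguably follows the listed criteria. That reading is fair and would leave the RLT count unaffected. It does not remove the contradiction on whether the patient is withdrawn, and the text does not say that this reading is the intended one. The 2% to 5% rate has no support in the documents. At 0.5% to 1%, one-arm stopping would be only 0.032 to 0.037.

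On infusion reactions, three sections (5.6.1, 5.7.3, 5.10) favour stopping, while 5.8.4 offers treatment guidelines and still has a role for grade 2 pain and for events not judged related. Section 5.8.4 also expects reactions to be infrequent, requires bedside monitoring, and gives no more drug at that visit if symptoms recur. All of this is true, and the documents give no rate of harm. But 5.8.4 goes beyond acute care: it directs re-infusion at the same visit and prepares for later ones. It is headed as management of reactions to varlilumab, so few of its grade 2 cases other than pain would be judged unrelated. The conflict therefore stands for most of the patients that 5.8.4 addresses.

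**Conclusion.** Both conflicts hold in the current text. The infusion conflict must be corrected because staff have opposite instructions on re-exposing a patient after the same event: 0 further infusions, or resumption plus up to 4 more. It does not change the RLT count, since the event is an RLT under 5.6.1 whatever 5.8.4 says.

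The delay conflict alone would be a lesser correction. It leaves the co-primary classification and the removal of a patient delayed 5 to 6 weeks open. It would change a one-arm stopping decision in about 1% to 7.5% of cases, assuming a pRLT of 0.05 and 2% to 5% of patients with such a delay counted as RLT. The top of that range is an upper limit.

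**What to change.** - Make 5.6.1 the only RLT definition, and change the delay text in 9.1.1 to its limit of more than 6 weeks.
- State one attribution condition for delay RLTs, so that purely logistic delays are not counted as toxicity. The discontinuation rules in 5.7.1 and 5.7.3 may keep a different condition.
- Revise 5.8.4 so that a related grade 2 infusion reaction (except grade 2 pain) is not re-infused, and keep the restart text only for grade 2 events that are not RLTs. If the sponsor intends re-infusion, change 5.6.1 to match.
- Correct the pointers to 5.3 (in 4.1) and 5.3.1 (in 5.7.1, 9.1.1 and 12.1.1) to 5.6.1.
- Classify patients already treated under the single definition. A separate line for delay-only RLTs in the RLT table would help the reader but is optional.

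The cost is one protocol amendment with IND and IRB review, because a safety definition and a dosing instruction change. No extra patients or tests are needed, and reclassification uses existing dosing dates and adverse event records.

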9.1.2 Immunogenicity

To evaluate the response rate and magnitude of CD4⁺ and CD8⁺ T-cell responses against IMA950 peptides in pre- and post-vaccine PBMC using the novel 2D multimer flow-cytometric analysis. We will also perform ELISPOT assays to evaluate the functional status of the antigen-specific T cells as cytokine-expression, and we are particularly interested in Type-1 (i.e. IFN- γ expressing) T cell response. While we use 2D multimer assay as the primary assay for its superior sensitivity, we will also use IFN- γ ELISPOT as the secondary assay for the immunological endpoint. We will determine whether Arm 1 patients demonstrate higher response rate and/or magnitude of response compared with Arm 2 patients.

9.2 Exploratory Objectives

As this study is not sufficiently powered to evaluate the following endpoints, data will be tabulated.

9.2.1Evaluation of IMA950-reactive T-cell infiltration and CXCL9/10 expression in tumors resected from Arm 1 and Arm 2 patients

12 April 2020 Page 63 of 88 confidential

In surgically resected tumor tissues from Arm 1 (IMA950+poly-ICLC and varlilumab) and Arm 2 (IMA950+poly-ICLC alone) patients, we will evaluate numbers of tumor-infiltrating CD4+ T-cells CD8+ T-cells (by flow-cytometry) and CXCL10 expression (by RT-PCR). Among T-cells, we will evaluate IMA950-reactive populations by flow-cytometry. We will perform preliminary comparisons of these readouts between Arm 1 and Arm 2 patients. In our separate vaccine study using GBM6-PD lysate (IRB# 15-17078 vaccine study), there will be samples from the control group who received no therapy prior to surgery. Hence these samples will be also used to assess whether IMA950+poly-ICLC vaccine in the current study (and varlilumab in Arm 1) increases the number of T-cells in the tumor site.

9.2.2 To evaluate IMA950-reactive T-cell receptor (TCR) clonotypes in tumors resected from Arm 1 and Arm 2 patients

While studies in 9.2.1 will provide us with actual numbers of vaccine-reactive T-cells, we may not obtain sufficient (i.e. at least 1 x 106 tumor-infiltrating lymphocytes) numbers of Tcells to obtain reliable data. As a more sensitive approach, we will utilize a novel method developed by Adaptive Biotechnologies (ImmunoSEQTM) that simultaneously amplifies and sequences tens of thousands of rearranged T-cell receptor (TCR) complementaritydetermining region 3 (CDR3)63 in each of PBMCs as well as tumor tissue. Because the technology utilizes genomic DNA, the frequency of sequenced CDR3 chains is representative of the relative frequency of each CDR3 sequence in the starting population of T-cells. Clones identified in the activated T-cells will be tracked in both PBMC and tumor. To evaluate IMA-950 reactive T-cell populations with this method, first, from postvaccine PBMC, we will isolate IMA-950-multimer positive populations using and flowcytometry sorting, and will evaluate usage of CDR3 chain clones in these populations. Then, we will evaluate the presence of the same CDR3 sequences in tumor tissue, which would indicate the presence of IMA-950-reactive T-cells in the resected tumor. Like 9.2.1, we will perform preliminary comparisons of this readout between Arm 1 and Arm 2 patients as well as the historical control group who received no therapy prior to surgery.

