1.2 Exploratory Objectives

1.2.1 To evaluate whether resected tumors from Arm 1 patients demonstrate significantly higher levels of IMA950-reactive T-cell infiltration and CXCL9/10 expression compared with those resected from Arm 2 (and/or the historical control patients who were enrolled in IRB# 15-17078 vaccine study).

- 1.2.2 To evaluate whether resected tumors from Arm 1 patients demonstrate significantly higher frequencies of IMA950-reactive T-cell receptor (TCR) clonotypes compared with those resected from Arm 2 (and/or the historical control patients who were enrolled in IRB# 15-17078 vaccine study).
- **1.2.3** To estimate overall survival (OS) and progression-free survival (PFS). PFS evaluation will use the Response Assessment in Neuro-Oncology (RANO) response criteria for diffuse low-grade glioma (LGG)2.
- **1.2.4** To evaluate whether PBMC responses against IMA950 are associated with PFS and frequency of IMA950-reactive T-cells in the tumor.
- **1.2.5** To tabulate tumor objective response rate (ORR) according to LGG RANO2, if there is measurable tumor.
- 1.2.6 To evaluate phenotype of leukocytes in PBMC samples. We will evaluate the phenotype (activation and exhaustion markers) on IMA950-reactive T-cells and the numbers of regulatory leukocyte subsets such as immature myeloid cells (IMCs), CD4+ T cells, CD4+/Foxp3+ regulatory T cells in both tumors and PBMCs in an exploratory manner.
- **1.2.7** To evaluate the pharmacokinetics (PK) for varillumab.

2 Background

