2.5 IMA950 as a novel, multi-peptide glioma vaccine

The IMA950 vaccine was developed by Immatics and European academic investigators¹, and includes 12 peptides, 9 human leukocyte antigen (HLA)-A*02 class I epitopes, an elongated class I epitope, one class II epitope, and the synthetic Hepatitis B virus marker peptide IMA-HBV-001. Peptides presented at the cell surface reflect the protein content of the cell; those on HLA class I molecules comprise the critical peptidome elements interacting with CD8+ T-cells. From *ex vivo* (i.e. surgically resected but not cultured) HLA-A*02+ GBM tissue, they eluted >3,000 HLA-A*02-restricted peptides, then selected 10 GBM-associated antigens based on the following criteria: 1) high expression in tumors; 2) very low or absent expression in healthy tissues; 3) implication in gliomagenesis, and 4) immunogenicity. Patients' CD8+ T-cells that were stimulated with IMA950 peptides *in vitro* specifically killed tumor cells. Further, CD8+ T cells infiltrating GBM tissue (without vaccine) recognized IMA950 antigens.¹

IMA950 was investigated in a first-in-man study sponsored by Cancer Research UK (CR-UK) in patients with newly diagnosed GBM (sponsor protocol number: CR0902-11, EUDRACT-2009-015971-28, NCT01222221). Enrollment of 45 patients started in October 2010 and has been completed in February 2013. This study compared vaccine-specific T-cell responses as a randomized two arm study. In cohort 1 at least the first 3 vaccinations were given before initial chemoradiotherapy (CRT), while in cohort 2, vaccinations started after completion of the standard-of care CRT but before the first cycle of maintenance TMZ. Patients received up to 11 vaccinations of IMA950 [plus granulocyte macrophage-colony stimulating factor (GM-CSF) in some vaccines] over 24 weeks (on day 1, 2, 3, 8, 22 and thereafter every 4 weeks). Of 23 analyzed patients, the vast majority showed CD8+vaccine-induced immune responses (91% immune responders, 57% multi-peptide responders). A mean number of 2.3 immune responses per patient have been observed so far in this trial.

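### The tumour TCR-clonotype comparison with untreated historical controls is not interpretable as written: the readout is built from blood drawn after IMA950 vaccination, which the documents do not provide for those controls

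*Combined protocol and SAP*

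**What the plan says.** **The readout.** Section 9.2.2 works in two steps. The clones of interest are first identified in blood taken after vaccination: from "PBMC, we will isolate IMA-950-multimer positive populations using and flowcytometry sorting". The tumour is then searched: "we will evaluate the presence of the same CDR3 sequences in tumor tissue". Section 8.4 describes the same source: "IMA950-specific multimer-positive T-cells in post vaccine PBMC will be sorted".

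**The comparison.** Section 9.2.2 plans, as a preliminary step, "comparisons of this readout between Arm 1 and Arm 2 patients as well as the historical control group who received no therapy prior to surgery". Objective 1.2.2 asks whether Arm 1 tumours show "significantly higher frequencies of IMA950-reactive T-cell receptor (TCR) clonotypes compared with those resected from Arm 2 (and/or the historical control patients" of IRB# 15-17078). The synopsis (exploratory objective 2) and section 8.4 carry the same historical contrast.

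**The controls.** Section 9.2.1 places them in a separate study of a GBM6-PD lysate vaccine, where "there will be samples from the control group who received no therapy prior to surgery". Section 8.4 describes the comparison set for vaccine-reactive T cells and CXCL10 as "HLA-A2+ patients who underwent resection under IRB# 15-17078 vaccine study".

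**The analysis.** Section 12.1.4 defines the readout as copies of vaccine-specific TCRs relative to total tumour DNA. It gives a t-test or Wilcoxon test for Arm 1 versus Arm 2 only. Section 12 gives no method for a historical comparison of this readout.

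**Background in unvaccinated tumour.** Section 2.5 reports that "CD8+ T cells infiltrating GBM tissue (without vaccine) recognized IMA950 antigens".

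**The concern.** A comparison between groups needs a measurement that can be taken in the same way in each group. Here the first step of the measurement, building the clone list, depends on blood drawn after IMA950. The controls did not receive IMA950 before surgery, and the documents describe no substitute list and no rule for scoring a control tumour.

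At stake is the historical half of objective 1.2.2. Because that objective is worded with and/or, it could be reported as met on the historical contrast alone. A difference in favour of the vaccine could then reflect how clones were looked for and not how many were in the tumour. Section 2.5 adds to the problem: unvaccinated glioma tissue can hold T cells that recognise these antigens, so a recorded zero in a control could not be read as a true absence.

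**Working it through.** The plan states no sample size, effect size or control count for this comparison, so there is no figure to reproduce. The check sets the definition against the control group, then illustrates the direction of the bias.

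**Step 1. What each group has, from 8.4, 9.2.1 and 9.2.2**

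| Element needed | Arms 1 and 2 | Historical controls |
|---|---|---|
| IMA950 before surgery | yes | no |
| Blood drawn after IMA950 | yes | none described |
| List of multimer-positive CDR3 sequences | yes | none described |
| Resected tumour | yes | yes |

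**Step 2. Two ways to score a control**

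- *Own-patient list.* This is the natural reading, although the documents do not state it. A control has no list, so the score is undefined. It becomes zero only if someone enters zero.
- *List pooled from Arms 1 and 2.* A treated tumour is searched with that patient's own clones as well as others'. A control tumour is searched only with other people's. Detection is equal only if the list finds as large a share of a control's reactive clones as of a treated patient's.

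**Step 3. Illustration under no true difference**

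Suppose the true tumour frequency of IMA950-reactive clones is the same in all groups. Let c be the fraction found by the list in treated patients and s the fraction found in controls. Both are assumptions. The apparent ratio is c / s.

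- c = 0.6, s = 0.01: 0.6 / 0.01 = 60
- c = 0.6, s = 0.05: 0.6 / 0.05 = 12
- c = 0.6, s = 0.10: 0.6 / 0.10 = 6
- c = 0.6, s = 0.20: 0.6 / 0.20 = 3
- Lowest over c = 0.3 to 0.9 and s = 0.01 to 0.20: 0.3 / 0.20 = 1.5
- Highest over the same range: 0.9 / 0.01 = 90

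**Step 4. How often a test would then favour the vaccine**

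The assumptions are 15 treated patients (one arm, from 12.1.2), 5, 10 or 15 controls, lognormal frequencies with log-SD 1, c = 0.6, a one-sided Wilcoxon test at 0.05, and 4,000 simulated trials per cell. The simulated false-positive rates are:

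| s | 5 controls | 10 controls | 15 controls |
|---|---|---|---|
| 0.05 | 1.00 | 1.00 | 1.00 |
| 0.10 | 0.94 | 0.99 | 1.00 |
| 0.20 | 0.62 | 0.81 | 0.89 |
| 0.60 (equal to c) | 0.05 | 0.05 | 0.05 |

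The nominal rate returns only when s equals c. The sizes depend on the assumed inputs. The direction needs only s below c.

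**Step 5. Definition of the control set**

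Section 8.4 requires HLA-A2+ but does not say that treatment before surgery excludes a patient. Sections 9.2.1 and 9.2.2 require no therapy before surgery but do not mention HLA type. The two restrictions are compatible, but no section states both. Trial patients must be HLA-A2+ (3.1.3), and nine of the twelve peptides are HLA-A*02 class I epitopes (2.5), so HLA type matters for the remaining historical comparisons too.

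**The case against.** The strongest reply is about weight. Section 9.2 says the exploratory endpoints are underpowered and will be tabulated. The synopsis and 9.2.2 call the comparison preliminary, and 12.1.4 tests Arm 1 versus Arm 2 only. No primary endpoint, stopping rule or sample size depends on it. All of that stands and limits the importance of the point. It does not rescue the contrast: small numbers excuse imprecision, but not a measurement that one group cannot supply. Objective 1.2.2 still speaks of significantly higher frequencies.

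A second reply is that control blood might exist and could be multimer-sorted. That is conceivable for HLA-A2+ patients, but the documents neither plan it nor say that such blood was kept. A list from unvaccinated blood need not find clones with the same sensitivity as one from vaccinated blood.

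A third is that infeasible and biased are different failures. This is correct. With own-patient lists the contrast is undefined. It is biased only if zeros are entered or a pooled list is used, and the documents prescribe neither.

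The fallback also has a weakness. Section 9.2.2 introduces the clonotype method because flow cytometry may not yield enough T cells from tumour for reliable data. The flow-cytometry comparison should therefore be made only where yield allows.

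**Conclusion.** The contrast between treated tumours and historical controls on the clonotype readout is not interpretable as written. The control score is undefined with an own-patient list and, with a pooled list, under-detected unless sequence sharing is complete. The size of the bias cannot be fixed from the documents because the sharing rate is unknown; the 1.5 to 90 range illustrates assumed values and is not an estimate. The section 2.5 finding concerns GBM, so it shows that a zero background cannot be presumed, not what the background is in grade II glioma.

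Three stronger readings go too far.

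- A reader might infer that the vaccine must look effective whatever happens. If few listed clones reach treated tumours, treated patients also score near zero, and no text says to enter zero for controls.
- A reader might infer that a pooled list would find almost nothing in controls because clonotypes are rarely shared. The documents say nothing about sharing.
- A reader might infer that Arm 1 versus Arm 2 is also invalid because varlilumab could lengthen the Arm 1 list. Both arms have post-vaccine blood, and the readout in 12.1.4 is copies per total tumour DNA, not a count of matched clones. More vaccine clones in the tumour is the effect being sought.

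The point is worth correcting, but it is confined to an exploratory contrast.

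**What to change.** 1. Delete the historical-control clonotype comparison from the synopsis (exploratory objective 2), 1.2.2, 8.4 and 9.2.2. Keep Arm 1 versus Arm 2 as in 12.1.4, which then matches the protocol text.
2. Keep the historical comparison only for readouts measured in the same way in both sets: CD4+ and CD8+ T-cell numbers, IMA950-reactive T cells by flow cytometry where cell yield allows, and CXCL10 expression.
3. Use one control definition throughout, combining 8.4 and 9.2.1: HLA-A2+ patients of IRB# 15-17078 with no therapy before surgery.

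The cost is a wording change. One exploratory contrast is lost, and fewer historical controls may qualify under the combined definition. The documents do not say how many, or whether the stored control tissue suits flow cytometry; both should be checked before the text is final.
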